## **8. Resource Sharing Plans**

All educational materials and questionnaires developed for this study (including REDCap templates) will be made available to the larger UF and scientific community. Genotype data will be available in EPIC, and thus can be accessed (deidentified) through the Integrated Data Repository (IDR) for future studies. As part of the IGNITE network, we are asked to share de-identified datasets with the other IGNITE network site investigators, primarily the IGNITE coordinating center, to be used for network wide analysis. Deidentified datasets may also be shared between UF and Nemours for cross site analysis for this project. We will include a section in the consent form that allows patients to choose whether or not to share de-identified genotype data with the National Institutes of Health using the dbGaP database. We will share PGX data and core phenotypes of interest with the larger scientific community through dbGaP if the parents and patients give permission for this type of data sharing.

## **9. Data Safety Monitoring Plan**

Based on assessments of the risk-to benefit ratio, the risk level associated with the study is low. All risks have been described in the consent form.

Monitoring for documentation of an adverse event, whether anticipated or unanticipated, is the responsibility of the principal investigator who will maintain oversight but may delegate collection of information related to this function to other study team members. In term of SAFETY monitoring, all adverse events spontaneously reported, elicited, or observed by the investigators will be recorded. All Serious Adverse Events, should they occur, whether study-related or expected, will be documented on a Case Report Form, under Adverse Event section in the Patient's binder, reported by the principal investigator to the IRB within five (5) working days.

In addition, the principal investigator will follow the reporting requirements for serious and unexpected adverse events outlined in the UF IRB Adverse Event Evaluation and Reporting Guide. All unanticipated, serious, fatal and/or life-threatening adverse events will be reported to

the UF IRB. Aggregate reports of adverse events will be prepared on an annual basis or at the end of the study, whichever may occur earlier and forwarded to the IRB at annual review.

**Plan for data management:** Case Report Form (CRF) within REDCap will be used for each subject. To protect the participant's right of privacy, subjects' individual records related to the study and will be stored in locked cabinets with limited access, and electronic files will be kept in secured database. A de-identified dataset from the database using a patient identification number will then be shared with statistician for analysis. During the study, data will be analyzed as it becomes available by [name] and the investigator team. No early closure is planned because of the limited scope and projected low risk of the study.

There is a prospect of direct benefit to individual subjects, in that genotype information could lead to improved patient outcomes.

Nevertheless, in the absence of a direct benefit, the study may advance the fields by provided an increased understanding of the utility of CYP2C19 genotyping for PPI dosing. Such understanding is deemed essential for broader dissemination of genotyping into clinical care.

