## 7. Research Plan:

The study is a randomized, open-label, comparative effectiveness clinical trial in 180 total patients with GERD or dyspepsia symptoms who will be randomized to either conventional or genotype-supported treatment of GERD and dyspepsia. A total of 120 patients will be enrolled in the UF Health Gastroenterology Clinics in Gainesville, and 60 will be enrolled in a parallel study (under separate IRB protocol) at Nemours Children's Hospital Gastroenterology Clinics in Orlando, FL. Each site will be responsible for overseeing patient care and research at their respective facility. All participants will have symptoms of GERD or related diseases and be candidates for PPI therapy or on PPI therapy with continued symptoms.

We will enroll a total of 180 patients between the UF Health and Nemours sites, which should allow for sufficient power to detect our efficacy endpoint (see power calculation below). We will also collect data from the health records for up to 24 months after enrollment on upper respiratory infection (cold), sore throat, strep throat, bronchitis, pneumonia, ear infection, acute sinusitis (sinus infection), bone fractures, renal function, and gastrointestinal infections for preliminary assessment of the effects of *CYP2C19*-supported PPI dosing on adverse effects. This exploratory arm will provide data to inform power calculations for a larger study focused on preventing PPI-associated adverse events through genotype-supported dosing.

**Inclusion Criteria.** A total of 120 patients with GERD or related symptoms will be enrolled at UF Health. An additional 60 patients will be enrolled at Nemours Children's Hospital Gastroenterology Clinics under a separate IRB protocol. For this protocol, any patient over the age of 17 who presents to GI clinic with GERD or related symptoms and is either 1) being initiated on PPI therapy or 2) continues to have symptoms despite PPI therapy will be considered eligible for the study.

Exclusion Criteria. This study will exclude patients who have had extensive esophageal or gastric surgery or any major chronic illness or condition that in the opinion of the gastroenterologist that would interfere with participation in the study.

Participant Recruitment Methods.

Prior to enrolling their patients, clinicians at participating GI clinics (investigators for this study) will be asked to complete surveys that assess their knowledge, attitudes, and beliefs as they relate to pharmacogenetics testing.

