Patients will be approached for participation at their GI clinic visit by the treating clinician and/or physician assistant. After providing informed consent, patients will be randomly assigned to either conventional treatment or genotype-supported PPI therapy using a randomization table. A 5-ml (one teaspoon) venous blood sample will then be drawn by a nurse, physician assistant, or phlebotomist. The patient will be asked to complete 3 surveys/questionnaires: the Reflux Disease Questionnaire (RDQ), Global Overall Symptom (GOS) scale, and a survey to assess knowledge, attitudes, and beliefs about pharmacogenetic testing. Patients will receive a total of \$25 for participating in this study. The \$25 VISA gift card will be provided after completing the final questionnaire. Patients in the control group may be withdrawn prior to completion if they or their physician elect to order the genetic test during the study. These patients would receive a \$10 VISA gift card for their participation up to the point of withdrawal.

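### The UF plan lets the investigator team, which includes the treating clinicians, analyse accruing data without excluding by-arm symptom results, which could influence dosing, control withdrawals and, if enrolment exceeds 12 weeks, recruitment

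*Combined protocol and SAP*

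**What the plan says.** The sentence stands in the UF protocol, section 9 (Data Safety Monitoring Plan), under the plan for data management. It says that, during the study, "data will be analyzed as it becomes available by" a redacted individual "and the investigator team. No early closure is planned because of the limited scope and projected low risk of the study". The preceding sentence gives a second route: "A de-identified dataset from the database using a patient identification number will then be shared with statistician for analysis". Neither sentence gives a schedule of looks, names the variables, or restricts the work to pooled or masked data.

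Section 7 (Research Plan) describes the people and the setting:

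- **Masking:** "The study is a randomized, open-label, comparative effectiveness clinical trial in 180 total patients".
- **Who the investigators are:** the recruitment paragraphs speak of "clinicians at participating GI clinics (investigators for this study".
- **Who recruits:** "Patients will be approached for participation at their GI clinic visit by the treating clinician and/or physician assistant".
- **Who sets the dose:** under genotyping and result reporting, the treating physician keeps the final say on prescribing, whatever the genotype recommendation.
- **Who may leave the control arm:** "Patients in the control group may be withdrawn prior to completion if they or their physician elect to order the genetic test" while the study is running.
- **Outcome:** RDQ and GOS are patient-reported and taken at baseline and 12 weeks.

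**The concern.** Read together, these statements give one group of people two roles. They may see results as they accrue, and they also take decisions that shape the results still to come. A clinician who has seen an early difference in symptom scores has a reason to manage control patients differently, or to order the test for a control who is doing badly. The first would dilute the contrast between arms. The second could remove controls selectively, and only controls have this exit. The bias could go in either direction and could not be separated out afterwards. Because the outcome is self-reported and unmasked, expectations raised by interim results could also affect the scores.

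The hypothesis is tested in a small group, about 30 rapid or ultra-rapid metabolizers per arm, so a few altered decisions would matter. No planned decision depends on an interim efficacy comparison, so nothing the plan needs is lost by waiting.

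**Working it through.** **1. Does the text permit by-arm symptom results to reach treating clinicians?** Section 9 names the investigator team as an analyst of accruing data. Section 7 places the clinic clinicians in that team and makes the trial open-label. Section 9 contains two partial safeguards. De-identification protects privacy, and the absence of a planned early closure deals with stopping. Neither keeps by-arm scores from clinicians. By-arm results are therefore not excluded, though they are not announced either.

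**2. When could such results exist?** No change score exists before a patient's week 12. Assume uniform accrual of 120 adults over E weeks. The share still to be enrolled when the first outcome arrives is max(0, 1 − 12/E). At that moment, a patient enrolled in week s has 12 − (12 − s) = s weeks of follow-up left.

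The Feasibility section supports three values of E:

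- 9 months, taken as 39 weeks
- 12 weeks, as forecast for the 120 adults
- 4 to 4.8 weeks, from its own inputs: 50–60 eligible per week, half consenting, gives 25–30 per week; 120/30 = 4 and 120/25 = 4.8

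| E (weeks) | Enrolled after first outcome | Follow-up left at week 12 |
|---|---|---|
| 39 | 1 − 12/39 = 69%, or 83 of 120 | up to 12 weeks for those already in; all 12 for the 83 to come |
| 12 | 0 | 0 to 12 weeks, mean 6 |
| 4–4.8 | 0 | at most 4–4.8 weeks, mean 2–2.4 |

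The recruitment route is open only on the 9-month timeline. The dosing and withdrawal routes are open on the 9-month and 12-week timelines, and largely closed on the shortest.

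**3. The plan's own power figure.** The sentence at issue carries no number. The nearest figure is the 80% power for an effect size of 0.74 in rapid and ultra-rapid metabolizers. Table 1 gives 28% + 5.3% = 33.3%, and 90 × 0.333 = 30 per arm. The noncentrality is 0.74 × √(30/2) = 2.87 on 58 degrees of freedom. At two-sided 0.05 (sidedness is not stated, so this is assumed), power is 80.5%. The figure reproduces.

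**4. How sensitive is that comparison?** The following losses and dilutions are assumed for illustration. They are not estimates of what interim looks would cause.

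| Assumed change | 10% | 20% | 30% |
|---|---|---|---|
| Controls lost from 30 (27, 24, 21 remain): power | 78.2% | 75.6% | 72.2% |
| Effect of 0.74 diluted (0.666, 0.592, 0.518): power | 71.8% | 61.6% | 50.5% |

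The first row counts lost numbers only and leaves out any selection among the controls who leave.

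**The case against.** The strongest reply is that the sentence says only data, in a paragraph on data management. The study also collects participation rates, surveys, acceptance of dosing recommendations and adverse events, and the team may have meant only these. The role of the redacted person is unknown, and a statistician receives a de-identified dataset. This stands to the extent that one cannot say by-arm outcomes will be analysed, only that nothing excludes them. If pooled data were meant, the fix simply records that.

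Second, clinicians already know the arm, see their own patients' symptoms, choose doses and can order the test. Those routes exist without any interim analysis and remain after the fix. This also stands. What interim results would add is the aggregate comparison, and its extra effect is not shown.

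Third, on the faster enrolment figures recruitment is complete before any outcome exists. This stands too, so the recruitment effect must be stated conditionally.

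A reader might also infer three stronger points that the documents do not support:

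- **Inflated type I error.** Unadjusted testing at 0.05 would give about 8% with two equally spaced looks and 14% with five, if any nominally significant look were reported. The plan specifies no interim test, no number of looks and no early reporting, and it foresees no early stop. Looking alone, with one final analysis, does not inflate the error rate.
- **Automatic removal of tested controls.** The text says they may be withdrawn, not that they will be.
- **A need to withhold by-arm adverse-event data.** The principal investigator is the only safety monitor the UF plan names, so such a ban would leave nobody reviewing safety by arm.

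**Conclusion.** The point holds as an avoidable route to operational bias, and as a cheap improvement. The plan states that the investigator team analyses data during the study. That team includes clinicians who recruit, prescribe and can trigger a control withdrawal, and by-arm RDQ and GOS results are not ruled out. Such results could influence dosing and control withdrawals. They could influence recruitment only if enrolment runs beyond 12 weeks; at 9 months with uniform accrual, about 83 of 120 adults would be exposed to that risk.

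The size of the bias cannot be derived from the documents. The power ranges in the working rest on assumed losses and dilutions and show only how sensitive a comparison of about 30 per arm is. The stated 80% power is arithmetically sound, and no type I error inflation follows unless an early nominal result is reported.

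**What to change.** Replace the sentence in section 9 with a statement along these lines: until the last 12-week questionnaire is in and the database is locked, no summary or comparison of RDQ or GOS by arm is produced for, or shown to, enrolling or treating clinicians; interim reports on recruitment, data quality and symptom scores are given with the arms combined. State that adverse-event monitoring by the principal investigator, serious adverse event reporting and the aggregate reports to the IRB continue unchanged.

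The Feasibility section should also settle which enrolment period applies, since the recruitment risk depends on it.

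The cost is one sentence of text and waiting until the end of follow-up for comparative efficacy results. No planned decision is lost. The change does not remove the influence of clinicians' knowledge of the arm or the control-only withdrawal route.

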## **10. Conflict of Interest:**

Publications that may result from such research can enhance the reputation of the investigators.

### **ABSTRACT**

Proton Pump Inhibitors (PPIs) are among the most commonly prescribed drugs in the world and are the agents of choice for the treatment of GERD and related conditions. While effective, PPI treatment fails in 40% of adults and children. The efficacy of PPIs is highly dependent on plasma concentrations achieved following drug administration. All PPIs are metabolized by the CYP2C19 enzyme located in the liver, which is encoded by the highly polymorphic CYP2C19 gene.

Depending on the CYP2C19 genotype individuals are classified into different phenotypes: poor metabolizer (PM), intermediate metabolizers (IM), normal metabolizers (NM), rapid metabolizer (RM) and ultra-rapid metabolizers (UM). Genetic variants in CYP2C19 are known to profoundly influence PPI plasma concentrations and therefore, response to PPI therapy. In addition to inadequate efficacy in some patients, short- and long-term use of PPIs has been associated with a number of significant adverse effects, including increased risk of intestinal and pulmonary infections, bone fractures and acute and chronic kidney disease, which may be influenced by CYP2C19 genotype.

Some of these adverse effects have been linked to increasing gastric acid suppression or higher than conventional PPI doses, and one randomized trial of PPI treatment for asthma reported a higher risk of respiratory infections among children phenotyped as IMs and PMs compared to NMs, RMs and UMs. These data support the hypothesis that genotype-guided dosing of PPIs would reduce treatment failures in RMs and UMs and minimize PPI-associated infections (and perhaps other adverse effects) in IMs and PMs. The overarching goals of this project are to use longitudinal, electronic health record (EHR) data to add to the body of evidence on PPI efficacy and safety by CYP2C19 genotype, and to document the feasibility and potential clinical benefits of CYP2C19 genotype-supported PPI dosing.

The overarching hypotheses are that PPI-associated adverse events are related to CYP2C19 variation and that genotype-supported dosing will reduce the risk of adverse events compared to conventional PPI dosing in adults and children. The aims of this project are (1) to define clinical outcomes in PPI-treated patients based on CYP2C19 genotype in a cross-network collaboration with Vanderbilt in 10,500 PPI-exposed patients with known CYP2C19 phenotypes; (2) to implement pharmacogenetic testing of the

CYP2C19 gene-PPI drug pair in adults at UF Health and in children at Nemours Children's Health System in the context of a comparative effectiveness genotype-supported vs. conventional PPI dosing trial; (3) In collaboration with Vanderbilt, using genotype and phenotype data in the EHR to conduct a genome-wide association study (PheWAS) on CYP2C19 genotype-inferred phenotype.

## **SPECIFIC AIMS**

Proton Pump Inhibitors (PPIs) are indicated for the treatment of gastroesophageal reflux disease (GERD), H.pylori infection, peptic ulcer disease, and gastric protection in patients at risk for gastrointestinal bleeding. PPIs are among the most commonly prescribed drugs in the world and their most common indication is GERD.

Refractory GERD is the term used to describe non-responsiveness to conventional PPI therapy, and it occurs in up to 40% of patients (both children and adults) even when the PPI dose is doubled. The efficacy of PPIs is highly dependent on plasma concentrations achieved following drug administration. All PPIs are metabolized in part by the CYP2C19 enzyme located in the liver, which is encoded by the highly polymorphic CYP2C19 gene.

Depending on the CYP2C19 genotype, individuals are classified into different metabolizer phenotypes: poor metabolizers (PM, 2 loss-of-function CYP2C19 alleles); intermediate metabolizers (IM, one loss-of-function allele); normal metabolizers (NM, no loss or gain-of-function alleles); rapid metabolizer (RM; one gain-of-function allele) and ultra-rapid metabolizers (UM, two gain-of-function alleles). Genetic variants in CYP2C19 are known to profoundly influence PPI plasma concentrations and therefore, response to PPI therapy. For example, individuals classified as either RM or UM have lower PPI concentrations compared to NM or of loss-of-function (LOF) allele carriers, respond poorly to PPI therapy and some fail to respond even when the PPI dose is doubled.

Short- and long-term use of PPIs has been associated with a number of significant adverse effects, which may be influenced by CYP2C19 genotype. Examples of serious adverse effects associated with PPIs included: 1) vitamin/mineral malabsorption associated with increased risk of bone fractures (calcium deficiency); 2) increased risk of intestinal infections (*Clostridium difficile* and small bowel bacterial overgrowth) and pulmonary infections (community and hospital-acquired), and 3) acute interstitial nephritis, chronic kidney disease and end stage renal disease; Some of these adverse effects have been linked to increasing gastric acid suppression or higher than conventional PPI doses. In a recent study reported by Dr.[name], children taking lansoprazole to treat poorly controlled asthma had a higher risk of infection compared to placebo, and the increased risk of infection was observed in IMs and PMs but not in NM, RM or UM patients.

These data support the hypothesis that genotype-guided dosing of PPIs would reduce treatment failures in RMs and UMs and minimize PPI-associated infections (and perhaps other adverse effects) in IMs and PMs. The overarching goals of this project are to use longitudinal, electronic health record (EHR) data to add to the body of evidence on PPI efficacy and safety by CYP2C19 genotype, and to document the feasibility and potential clinical benefits of CYP2C19 genotype-supported PPI dosing.

**Aim1:** Define clinical outcomes in PPI-treated patients based on CYP2C19 genotype. This aim will be conducted as a cross-network project with Vanderbilt, the other IGNITE site with substantial CYP2C19 genotype data in the EHR. Between the two institutions, we have CYP2C19 genotype data in the EHR on more than 16,000 patients, of whom more than 10,000 have exposure to a PPI. This provides significant power to test the influence of genotype on clinical outcomes with PPI use. The hypothesis is that PMs and IMs will have better control of GERD, but increased rates of adverse events (infection, bone fractures, adverse effects on kidney). In contrast, rapid metabolizers (RM and UMs) are more likely to develop refractory GERD and lower rates of PPI-related complications.

**Aim 2:** Implement pharmacogenetic testing of the CYP2C19 gene-PPI drug pair in adults at UF Health and in children at Nemours Children's Health System in the context of a comparative effectiveness genotype-supported vs. conventional PPI dosing trial. Given that PPI efficacy and adverse events are related to PPI exposure and to metabolizer phenotype, individualizing treatment using CYP2C19 genotype guided dosing is expected to improve patient outcomes. We hypothesize that genotype-guided PPI dosing will reduce the rates of infection, fracture, adverse kidney outcomes and evoke equivalent efficacy for GERD symptoms compared to conventional dosing in children and adults referred to Nemours Children's Hospital and UF Health. We will evaluate physician acceptance of genetic information into clinical practice and potential impact on clinical outcomes.

**Aim3.** Using genotype and phenotype data in the EHR, conduct a genome-wide association study (PheWAS) on CYP2C19 genotype-inferred phenotype. We will conduct this aim in collaboration with Vanderbilt University, who will lead the aim. Please see their proposal for specific details.

## **SIGNIFICANCE**

Currently, use of CYP2C19 genotype to guide PPI dosing is not recommended by either the American Gastroenterology Association or the American College of Gastroenterology. At UF Health, gastroenterologists have not used CYP2C19-guided PPI dosing and thus there is a need for education, further evidence generation, and a pilot implementation study. Nemours Children's Hospital has implemented a program whereby pediatric gastroenterologists can utilize CYP2C19 genotype-guided PPI dosing in children with GERD. The proposed study is significant because it may extend the evidence regarding influence of CYP2C19-genotype in PPI efficacy and safety, lead to more rationale dosing of PPIs, increase recognition of potential adverse events of PPI therapy and the ability to minimize them with genotype guided dosing, and build a body of evidence to facilitate the implementation of pharmacogenetic-guided PPI dosing.

**GERD Refractory to PPI Treatment.** Gastroesophageal reflux disease (GERD) affects 10-20% of adults and children in Western countries . PPIs are agents of choice to treat GERD, and are among the highest-selling classes of drugs in the US with \$9.5 billion in sales in 2015. Six PPIs are commercially available: omeprazole (Prilosec); lansoprazole (Prevacid), dexlansoprazole (Dexilant) esomeprazole (Nexium), pantoprazole (Protonix), rabeprazole (Aciphex). Low doses of omeprazole and lansoprazole can be purchased over the counter. The use of PPIs has increased dramatically during the past decade owing in part to the perception among clinicians that PPI treatment is safe and causes negligible side effects.

However, there are increasing safety concerns expressed by the FDA and others regarding the use and safety of PPIs in children and adults. While effective for symptom relief and erosive esophagitis, PPI treatment fails in up to 40% of adults and children with GERD. Failure to respond to standard, once daily PPI treatment or complete or partial response to twice daily PPI treatment has been defined as refractory GERD. Several factors have been associated with refractory GERD including adherence to PPI therapy, esophageal hypersensitivity and inter-individual differences in PPI metabolism^11. The present proposal focuses on differences in PPI metabolism as a mechanism underlying response to GERD symptoms and refractory GERD.

**CYP2C19 genetic variation influences the pharmacokinetics of PPIs.** PPIs inhibit the final pathway of acid production in gastric parietal cells by covalently binding to the H+/K+-ATPase proton pump leading to inhibition of acid secretion, which lasts for 24-48 hours despite the drug's short pharmacokinetic half-life. Most PPIs are metabolized by CYP2C19 and CYP3A4; have short elimination half-lives (1-4 hours) and distribution volumes that are 8%-20% of total body water. All PPIs have low hepatic clearances, low first-pass metabolism and have high bioavailabilities. The CYP2C19 gene that encodes the CYP2C19 enzyme is located on chromosome 10q24.1-q24.3, has 9 exons and is highly polymorphic. Several loss of function alleles (e.g., CYP2C19\*2 through \*9) reduce drug clearance and significantly increase PPI plasma concentrations and area under the plasma concentration-time curve (AUC). Carriers of one or two loss of function (LOF) alleles are referred to as intermediate and poor metabolizers (IMs and PMs), respectively.

The extent to which CYP2C19 variation affects clearance depends on the fraction of total clearance attributable to CYP2C19. All PPIs undergo significant metabolism by CYP2C19 and genetic variation in CYP2C19 influences the pharmacokinetics of all PPIs. The G681A polymorphism causes a splicing defect in exon 5 resulting in protein synthesis termination and is responsible for the \*2 allele, the most prevalent LOF allele. The wild type (WT) CYP2C19\*1 allele is the nomenclature assigned when no functional variant alleles are present, and is associated with a more rapid clearance and lower AUCs compared to the PM or IM phenotypes.

Those who are homozygous for \*1 are referred to as and are responsible for normal metabolizer (NM) phenotype. CYP2C19\*17 is a gain- of-function allele that increases the clearance of PPIs and reduces AUC compared to NMs. The \*1/\*17 or \*17/\*17 genotypes contribute to the rapid or ultra-rapid metabolizer phenotype (RM or UM, respectively). The AUC following the administration of equal PPI doses can vary 3-10 fold between PMs and UMs. **Table 1** shows population frequency data for the various genotypes/inferred phenotypes from the UF clinical implementation of CYP2C19 genotyping for clopidogrel response prediction.

